### 1.3.5 Indication

The NIMBUS is intended to be used to restore blood flow in patients experiencing an acute ischemic stroke due to a large vessel neurovascular occlusion. The Device is designed for use in the anterior and posterior neurovasculature in vessels of diameter 1.5 mm to 5.0 mm, such as the internal carotid artery, the M1 and M2 segments of the middle cerebral artery, the A1 and A2 segments of the anterior cerebral artery, the basilar, the posterior cerebral and the vertebral arteries.

The Device should only be used by physicians trained in neurointerventional catheterization and the treatment of ischemic stroke.

### 1.3.6 Endovascular procedure with NIMBUS

The endovascular treatment of stroke is performed per each institution's standard procedure according to the NIMBUS Instructions for Use (IFU), the inclusion/exclusion criteria, and to the procedures as outlined in this study protocol.

#### 1.3.6.1 Preparation & Delivery

Using standard interventional techniques, access the arterial system and using angiography, determine the location of the occluded vessel. Advance an appropriate Guide Catheter, Sheath or Balloon Guide Catheter as close to the occlusion site as possible. Connect a rotating hemostasis valve (RHV) to the proximal end of this catheter and connect to a continuous flush system.

With the aid of a suitable Guidewire, and using standard catheterization techniques and fluoroscopic guidance, an appropriately sized Microcatheter is advanced up to and across the occlusion so that the distal end of the Microcatheter is positioned distal to the occlusion. The guidewire is removed, and NIMBUS is inserted and advanced into the Microcatheter, with the use of the Insertion Tool.

#### 1.3.6.2 Positioning and Deployment

Continue to advance NIMBUS until the radiopaque distal markers approach the distal region of the Microcatheter. NIMBUS should be positioned in the clot ideally such that the end of the proximal radiopaque coil is aligned with the proximal face of the clot (Figure 3). To fully deploy NIMBUS within the clot, retract the Microcatheter until the distal tip of the Microcatheter is positioned over the proximal radiopaque coil of NIMBUS.

[figure not shown]

Figure 3: NIMBUS Positioning

#### 1.3.6.3 Retrieval

Prior to clot retrieval re-advance the Microcatheter to the clot while holding NIMBUS push wire static until resistance is met. Do not continue to advance against significant resistance. Withdraw NIMBUS and Microcatheter slowly and carefully as a single unit to the Guide Catheter while aspirating through the guide, and maintaining Microcatheter and NIMBUS position relative to each other during the withdrawal step. Applying vigorous aspiration (by syringe), withdraw NIMBUS and Microcatheter into the Guide Catheter and continue to aspirate until NIMBUS reaches the RHV on the guide. Disconnect the RHV from the guide and remove NIMBUS, Microcatheter and RHV together from the guide.

### 1.3.6.4 Cleaning and Re-use

NIMBUS may be used for up to three retrieval attempts. If an additional pass is to be made with NIMBUS, then carefully remove any captured thrombus from NIMBUS, and clean NIMBUS in heparinized saline, rubbing gently from proximal to distal to remove any residual thrombus material. Then, follow the same preparation, delivery, and retrievals steps, as described in the NIMBUS IFU. Do not attempt more than three retrieval attempts in one vessel.

## 1.4 Potential Risks and Benefits

The risks and benefits of participating in the study will be explained in the voluntary written informed consent that must be obtained from all subjects.

### 1.4.1 Contraindications

- Allergy or hypersensitivity to Nickel-Titanium.
- Excessive vessel tortuosity that may prevent device delivery.
- Patients with angiographic evidence of carotid dissection.

### 1.4.2 Potential Complications

Risks that may be associated with the use of NIMBUS can be found in the commercially available IFUs found with the device.

### 1.4.3 Potential Benefits from use of NIMBUS

Although there may be no direct benefits of study participation, subject participants records will undergo an enhanced level of clinical scrutiny compared to routine SOC, which may provide some indirect health benefits. The potential benefits of this commercially approved device outweigh any anticipated risks.

## 2 OBJECTIVES AND PURPOSE

The objective of this study is to assess the efficacy of NIMBUS in a real-world setting in patients where the first one or two passes with another Mechanical Thrombectomy therapy have not achieved mTICI 2b or better.

The rate of effectiveness achieved will be considered as we design further studies. The study will also report on clot characteristics and clinical outcomes.

## 3 STUDY DESIGN, ENDPOINTS, AND OTHER ANALYSES

### 3.1 Description of the Study Design

This is a prospective, multi-center, single-arm, observational post market study that will consecutively enroll up to 50 subjects treated with NIMBUS at approximately 10 sites in Europe. This study will evaluate NIMBUS, post one or two unsuccessful passes of another Mechanical Thrombectomy device, in the treatment of acute ischemic stroke. Data will be collected at baseline (prior to thrombectomy), during the procedure, and post-procedure. Clinical follow up with subjects will occur over 3 months; at 24 hours, and 90 days post procedure.

### 3.2 Study Endpoints

#### 3.2.1 Primary Endpoint

##### 1. Successful Revascularization (mTICI $\geq$ 2b) with NIMBUS as determined by an Independent Core Lab.

The primary endpoint is successful revascularization after the final pass of NIMBUS, as determined by an Independent Core Lab, where the successful revascularization is defined as achieving an mTICI score of 2b or greater. In this study, revascularization will be measured by an independent adjudicating Imaging Core Lab and reported using the Expanded Thrombolysis in Cerebrovascular Infarction (eTICI), inclusive of the 2C rating (Table 2). For purposes of data comparisons, a minimum threshold of mTICI 2b is equal to eTICI 2b50.

**Table 2: eTICI inclusive of the 2c rating**

eTICI (inclusive of the 2C rating) scale [31, 32, 33, 34, 35]	
0	No reperfusion; 0% filling of the downstream territory.
1	Thrombus reduction without any reperfusion of distal arteries.
2	2a Reperfusion in less than half (1-49%) of the territory. 2b50 Reperfusion in (50-66%) of downstream territory. 2b67 Reperfusion in (67-89%) of downstream territory. 2c Reperfusion in (90-99%) of downstream territory.
3	Complete or 100% reperfusion.

#### 3.2.2 Secondary Endpoints

The secondary endpoints are pre-specified below and have been identified as outcomes meaningful to evaluate the effectiveness and safety of stroke treatment with NIMBUS.

##### 1. Successful Procedural Revascularization (final mTICI $\geq$ 2b)

Rate of achieving an mTICI score of 2b or greater (Table 2) at the end of the procedure, as determined by an Independent Core Lab.

##### 2. Excellent Procedural Revascularization (final mTICI $\geq$ 2c)

Rate of achieving an mTICI score of 2c or greater (Table 2) at the end of the procedure, as determined by an Independent Core Lab.

##### 3. First Pass Revascularization using Nimbus (mTICI $\geq$ 2b)

Rate of achieving an mTICI score of 2b or greater (Table 2) after the first use of NIMBUS (whether on the second or third pass), as determined by an Independent Core Lab.

##### 4. Occurrence of Embolization to a New Territory (ENT)

Rate of embolization in a previously unaffected territory, following the final pass of NIMBUS.

## 5. Symptomatic Intracerebral Hemorrhage (sICH) at 24 hours specified according to the Heidelberg Bleeding Classification (HBC)

Rate of sICH at 24 hours post-procedure. Symptomatic Intracerebral Hemorrhage (sICH) is defined per the Heidelberg Bleeding Classification (Table 3).

**Table 3: Definition of Symptomatic Intracerebral Hemorrhage**

Heidelberg Bleeding Classification (HBC) [36]

SICH: new intracranial hemorrhage detected by brain imaging associated with any of the item below:
 
 
• <math>\geq 4</math> points total NIHSS at the time of diagnosis compared to immediately before worsening. Note that a 4 points change is not compared with the baseline admission NIHSS score but instead to the immediate predeterioration neurological status.
 
• <math>\geq 2</math> point in one NIHSS category. The rationale for this is to capture new hemorrhages that produce new neurological symptoms, making them clearly symptomatic but not causing worsening in the original stroke territory. For example, a new remote hemorrhage in the contralateral occipital lobe may cause new hemianopia that is clearly symptomatic but the patient will not have worsening of <math>\geq 4</math> points on the NIHSS score.
 
• Leading to intubation/hemicraniectomy/EVD placement or other major medical/surgical intervention.
 
• Absence of alternative explanation for deterioration.
 

## 6. 90 Day All-Cause Mortality

Rate of all-cause mortality at 90 days post-procedure.

## 7. Modified Rankin Scale (mRS) of $\leq 2$ at 90 days

Rate of independence (mRS of  $\leq 2$ ) at 90 days post-procedure.

### 3.3 Ancillary Endpoints

#### 3.3.1 Clot Analysis

**Histopathologic analysis of Clot Collected** – Composition of clot components, per pass, to be evaluated including: Red Blood Cells (RBC), White Blood Cells (WBC), platelets, fibrin and other proteins, as evaluated by the independent Central Lab.

#### 3.3.2 Hospitalization Analysis

Medical Resource Utilization and Health Economics related data including:

1. Hospitalization length of stay for index procedure and unscheduled re-hospitalizations.
2. Healthcare resource utilization for index procedure, post-procedure and re-hospitalizations for unscheduled events.

## 4 STUDY POPULATION

Prior to inclusion in the study all subjects will be screened for study eligibility. Therefore, clinical site personnel will review the subject's medical history.

#### 4.1 Inclusion Criteria

Prior to entry in this study, patients must meet **ALL** of the following criteria:

1. Age  $\geq$  18.
2. The subject or the subject's legally authorized representative has signed and dated an Informed Consent Form.
3. Patient has had one or two passes of another mechanical thrombectomy device without achieving mTICI 2b or better and continues to have angiographic confirmation of a Large Vessel Occlusion (LVO) in the same vessel.
4. mRS 0-1 prior to this stroke.
5. NIMBUS is used on the second or third overall pass to attempt revascularization.

#### 4.2 Exclusion Criteria

Patients must be excluded from this study if **ANY** of the following criteria are met:

1. Currently participating in an investigational (drug, device, etc.) clinical trial that may confound study endpoints. Patients in observational, natural history, and/or epidemiological studies not involving intervention are eligible.
2. Confirmation of positive pregnancy test according to site specific standard of care (e.g. test, verbal communication).
3. All patients with severe hypertension on presentation (SBP  $>$  220 mmHg and/or DBP  $>$  120 mm Hg). All patients, in whom intravenous therapy with blood pressure medications is indicated, with hypertension that remains severe and sustained despite intravenous antihypertensive therapy (SBP  $>$  185 mmHg and/ or DBP  $>$  110 mmHg).
4. Known cerebral vasculitis.
5. Known cancer with life expectancy less than 12 months.
6. Stenosis, or any occlusion, in a proximal vessel that requires treatment or prevents access to the site of occlusion.
7. Intracranial stenosis that prevents access to the site of occlusion.
8. Computed tomography (CT) or Magnetic Resonance Imaging (MRI) evidence of recent/ fresh hemorrhage on presentation.
9. Baseline computed tomography (CT) or MRI showing mass effect or intracranial tumor (except small meningioma).
10. Evidence of dissection in the extra or intracranial cerebral arteries.
11. Occlusions in multiple vascular territories (e.g., bilateral anterior circulation, or anterior/posterior circulation).

#### 4.3 Study Duration

The duration of the study is expected to be approximately 33 months. This includes an enrolment period of approximately 30 months and a post-treatment follow-up evaluation of 3 months.

#### 4.4 Number of Subjects

Up to 50 subjects will be consecutively enrolled into the study which will involve treatment with the NIMBUS device.

A minimum of 3 subjects will be enrolled per site, to ensure generalizability of results and to minimize the influence of any single site, no more than approximately 25% of the total enrollment will be allowed at a single site (i.e., a maximum of 12 subjects enrolled per site).

#### **4.5 Number of Sites**

The study will be conducted at approximately 10 institutions in Europe where NIMBUS is approved for commercial use.

#### **4.6 Participant Withdrawal or Termination**

##### **4.6.1 Reasons for Withdrawal or Termination**

Subjects are free to withdraw from participation in the study at any time upon request. The investigator may terminate participation in the study if any adverse event or other medical condition or situation occurs such that continued participation would not be in the best interest of the participant.

##### **4.6.2 Handling of Participant Withdrawals or Termination**

Subjects that withdraw consent after treatment are not required to undergo follow-up after withdrawal. They will not be replaced and will be considered part of the subject cohort. The reason for early withdrawal will be documented in the source documents and case report forms.

In the event a subject withdraws from the study, their data will be excluded from the data analysis from the time of withdrawal going forward. All data collected prior to withdrawal will be included in for data analysis, as permitted per country regulations.

### **5 STUDY PROCEDURES AND EVALUATIONS**

#### **5.1 Study Specific Procedures**

All procedures are expected to follow the standard of care of the sites participating in this study.

#### **5.2 Standard of Care Procedures**

The procedures completed as part of this study are standard practice and include collection of relevant medical history, relevant medication history, neurological examination, NIHSS, mRS, imaging (e.g., CT and/or MRI), and review of any AEs. This may vary from site to site.

#### **5.3 Independent Core Laboratory for Image Evaluation**

All imaging collected will be SOC, no additional imaging will be requested for this study. Imaging should include full A-P lateral images for the start and the end of each procedural pass. An independent radiographic core laboratory shall be utilized to provide an unbiased and standardized assessment of all collected imaging. All subject protected health information will be removed before an image is uploaded and evaluated. The core lab assessor will be blinded to subjects' previous medical history. Each angiogram will be read independently by experienced Imaging Core Lab neuro-interventionalists.

The objective of the Imaging Core Lab will be to:

- Review all angiograms obtained
- Provide an unbiased assessment of the rate of revascularization defined by mTICI scores based on angiographic imaging from the study sites
- Evaluate CT/MRI examinations to detect and assess hemorrhages.

This study will be collecting the following imaging data to be assessed by Imaging Core Lab:

- Baseline - CT/ MR imaging
  - Infarct volume
  - Clot location
  - Clot length
  - Clot radiodensity on CT / Susceptibility Vessel Sign (SVS) on MRI
- Procedural Angiography
  - mTICI score for every pass
  - Clot location for every pass (proximal face of clot)
  - Emboli to new territories
- Post Procedure - CT/ MR imaging
  - Intracranial Hemorrhage

Hemorrhages will be classified according to the following categories [36]:

- HI 1 – Scattered small petechiae, no mass effect
- HI 2 – Confluent petechiae, no mass effect
- PH1 – Hematoma within infarcted tissue, occupying <30%, no substantive mass effect
- PH2 – Hematoma occupying 30% or more of the infarcted tissue, with obvious mass effect
- RIH – Parenchymal hematoma remote from infarcted brain tissue
- IVH – Intraventricular Hemorrhage
- SAH – Subarachnoid Hemorrhage
- SDH – Sub Dural Hemorrhage

### 5.3.1 Imaging Shipment

De-identified images may be sent via DICOM format on a CD (that contains the subject ID, study visit, Sponsor name, and protocol number), or electronically to the core lab website, if available.

## 5.4 Clot Collection and Processing

Normally, following mechanical thrombectomy, the retrieved clot is discarded. However, for subjects in this study, clot will be collected for follow on analysis. Sites will place the clot collected per pass in a container of neutral buffered formalin solution for preservation. If more than one clot fragment is retrieved during different retrieval attempts / passes, the fragments will be collected per pass into separate containers. Each container will have a unique subject identifier noting the retrieval attempt / pass number on the label. This unique identifier will be entered in the eCRF by the site along with other relevant data and linked to the subject ID. Samples will subsequently be shipped by the site to the independent Central Lab for follow on analysis (Section 5.4.1).

All materials for collecting, processing and shipping samples to the independent Central Lab will be provided by the Sponsor or the Sponsor's selected vendor. For additional details on sample processing refer to Clot Collection and Processing Manual provided by CERENOVUS.

#### **5.4.1 Independent Central Lab for Clot Evaluation**

Clot materials collected for this study will be processed by the independent Central Lab. Standardized procedures and techniques have been established by the independent Central Lab for the analysis of AIS clots. These techniques comprise of morphological and histological testing, which will help in defining clot features and clot compositional analysis for this study.

Samples will be stored until the research and development testing is completed or the sample is completely used. Leftover specimens not used in the immediate research will be stored for future use in research that will aid in understanding the etiology of the disease.

### **5.5 Neurological Evaluations**

The following neurological evaluations will be used in this study and are part of SOC:

**NIHSS Score** - The National Institutes of Health Stroke Scale, or NIH Stroke Scale (NIHSS) is a tool used by healthcare providers to objectively quantify the impairment caused by a stroke. The NIHSS is composed of 11 items, each of which scores a specific ability between a 0 and 4. For each item, a score of 0 typically indicates normal function in that specific ability, while a higher score is indicative of some level of impairment. The individual scores from each item are summed in order to calculate a subject's total NIHSS score. The maximum possible score is 42, with the minimum score being a 0.

**The modified Rankin Scale (mRS)** - The mRS is a scale commonly used to measure the degree of disability or dependence in the daily activities in subjects following stroke or other neurologic event and is conducted by a qualified evaluator. It is a scale with seven categories ranging from no symptoms to severe disability and death. Qualifications of evaluator training will be documented for this study. The 90 day mRS must be performed by a qualified independent evaluator who is not part of the interventional treating team.

## **6 STUDY SCHEDULE**

Study subjects will be managed by the respective Investigators and his/her staff according to the current standard procedures at each participating study site. Data will be collected according to the defined schedule listed in Table 1.

### **6.1 Screening**

Subjects presenting with AIS to the enrolling medical treatment facility will be evaluated and treated by the physician according to the institutional practice prior to enrolment in the study. A subject can be consented to participate in this study from the point of imaging confirming a large vessel occlusion up to 7 days post-procedure. Subjects will be screened against the study inclusion/exclusion criteria to determine their initial eligibility. The final eligibility criterion is the requirement for a second pass of a mechanical thrombectomy device during the index procedure, therefore, the screening log should be completed post procedurally for all AIS patients in whom a second mechanical thrombectomy pass was completed. All subjects screened will be documented on the Screening/Enrolment log, including the reason for non-participation for subjects who do not enroll.

All assessments and imaging performed for this study are part of SOC for stroke treatment. Informed consent is mandatory and must be obtained before any data is captured in the eCRF.

During the eligibility screening, the investigator will perform an initial evaluation of potential study subjects for study eligibility according to inclusion / exclusion criteria. For subjects who meet the eligibility criteria and agree to participate, informed consent will be obtained. The investigator, or designee, will explain the research study to the subject and/or the legally authorized representative and answer any questions that may arise. The possible risks and possible benefits of participation will be discussed. The subject and/or the legally authorized representative will be asked to read, review and sign the EC approved informed consent form. The informed consent process is detailed further in Section 10.3.

**A subject is considered enrolled in this study after the physician confirms the subject meets all eligibility criteria, and the subject is consented.**

All subjects *who provide written informed consent* will be entered into eCRF regardless of whether or not they participate in the study.

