### 7.3 Time Period and Frequency for Adverse Event Assessment and Follow-up

AEs shall be assessed and documented for all enrolled eligible subjects from the start of the procedure or time of consent, whichever is earlier, to the end of the study participation or until their withdrawal, whichever occurs first. AEs will not be collected by the Sponsor until after consent is obtained from the subject and/or the legally authorized representative. AEs that occur during this study should be treated by established standards of care which will protect the life and safety of the subject. Events will be followed for outcome information until resolution, stabilization or the subject exits the study, whichever occurs first. Each investigator shall provide source documentation as requested by the Sponsor to facilitate reporting and adjudication of these events.

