### 9.7.2 Disposition of Study Subjects

The number and percentage of subjects in the mITT Analysis Set, together with a summary of subjects who were excluded (i.e. ineligible consented subjects), completed or discontinued the study with associated reasons, will be summarized for all consented subjects.

Enrollment by site will be summarized for all enrolled subjects.

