## **13 PROTOCOL DEVIATIONS**

The investigator is responsible for ensuring that the clinical investigation is conducted in accordance with the procedures described in the protocol, and any conditions required by the reviewing EC. A protocol deviation is a failure to comply (intentionally or unintentionally) with the requirements of the clinical study

as specified in the protocol. Examples of protocol deviations include late visits, missed visits, required follow-up testing not completed, visit out of window, non-adherence to inclusion/exclusion criteria, etc. and shall be reported to the Sponsor through the eCRFs. Deviations will be reviewed and assessed by the Sponsor.

It is the responsibility of the site to use vigilance to identify and report deviations to the Sponsor and EC per guidelines. The study monitors shall verify that the conduct of the study is in compliance with the approved protocol and applicable regulations and shall identify deviations and any issues of noncompliance. Corrective and preventative actions will be implemented promptly as necessary and significant protocol deviations that raise subject safety concerns or indicate repeat noncompliance may be grounds for investigator disqualification and/or reporting to the regulatory authorities.

The investigator is not allowed to deviate from the protocol except under emergency circumstances to protect the rights, safety and well-being of study participants. Under emergency circumstances, deviations from the protocol to protect the rights, safety and well-being of human subjects may proceed without prior approval of the sponsor and the ethics committee. Such deviations shall be documented and reported to the sponsor and ethics committee as soon as possible.

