## 5 Analysis Sets

The following analysis sets are defined in the study:

- **Modified Intent-to-Treat (mITT) Analysis Set**

The mITT Analysis Set consists of all subjects who are enrolled into the study, and who have attempted at least one pass with the NIMBUS device (which includes deployment and retrieval with the NIMBUS device).

A subject is considered enrolled in this study after the physician confirms the subject meets all eligibility criteria, and the subject is consented.

- **mRS Analysis Set**

The mRS Analysis Set consists of all mITT subjects who meet the study criteria as defined in protocol section 9.5.

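### Consented, NIMBUS-exposed subjects who are not confirmed eligible after the procedure fall outside mITT and the named AE population, and no planned endpoint analysis covers them

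*Protocol*

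**What the plan says.** Protocol 6.1 (Screening), repeated under the mITT definition in SAP 5, sets two conditions for enrolment: "A subject is considered enrolled in this study after the physician confirms the subject meets all eligibility criteria, and the subject is consented". The same Protocol section says that patients are "treated by the physician according to the institutional practice prior to enrolment in the study". It gives this consent window: "A subject can be consented to participate in this study from the point of imaging confirming a large vessel occlusion up to 7 days post-procedure". It also says that "the screening log should be completed post procedurally for all AIS patients in whom a second mechanical thrombectomy pass was completed". Inclusion criterion 5 (Protocol 4.1) is use of NIMBUS on overall pass two or three.

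The analysis population follows from enrolment. SAP 5: "The mITT Analysis Set consists of all subjects who are enrolled into the study, and who have attempted at least one pass with the NIMBUS". The only other set, the mRS Analysis Set, is a subset of mITT.

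For safety, Protocol 7.3 says: "AEs shall be assessed and documented for all enrolled eligible subjects". Protocol 9.7.2 expects some consented subjects to be left out, since it asks for "a summary of subjects who were excluded (i.e. ineligible consented subjects"). SAP 7.2 keeps the summary of completed and discontinued subjects but not that one. Protocol 13 gives "non-adherence to inclusion/exclusion criteria" as an example of a deviation, and SAP 7.10 summarises deviations in mITT.

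**The concern.** Criterion 5 cannot be met until NIMBUS has been used, so confirmation of all the criteria is only complete after exposure. The documents set no time by which it must be made and do not require it before the angiographic result is seen. Protocol 6.3 has the site record mTICI before and after each pass, so the operator's own reading is available by then.

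A consented subject who received NIMBUS and is refused at confirmation is not enrolled and therefore not in mITT. ENT, sICH, mortality and the primary rate are all planned in mITT or its subset, and SAP 7.10 lists device deficiencies in mITT. For harms, the natural denominator is everyone exposed who consented, and the plan has no such set. In a study of about 50 subjects, one or two events outside the denominator are visible in a rate for a rare outcome.

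**Working it through.** **The plan's own figure.** Protocol 9.6 and SAP 6: 50 enrolled, 10% attrition, so 50 × 0.90 = 45; assumed rate 86%. Margin = 1.96 × √(0.86 × 0.14 / 45) = 10.14%, which reproduces the stated 10.1%. This figure is not in dispute; it serves as a yardstick.

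**Following one subject through the text.** Take a patient who consents, receives NIMBUS, and is then not confirmed eligible.

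1. Enrolled? No: Protocol 6.1 and SAP 5 need the confirmation.
2. In mITT? No: it holds enrolled subjects only. In the mRS set? No: it is a subset of mITT.
3. In the AE population of Protocol 7.3? No: it names enrolled eligible subjects.
4. Recorded anywhere? Yes. Protocol 6.1 enters every consenting subject in the eCRF and logs reasons for non-participation.
5. Visible in the SAP? As a count only. SAP 7.2 summarises enrolment by site for all consented subjects and for each analysis set, so the difference can be derived, but not the reasons or outcomes.
6. In an endpoint analysis? None is planned. SAP 7.6 names no population for the AE tables.

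Now take a patient who is confirmed and consented, and is then found to breach a criterion. This subject is already enrolled, no rule provides for reversing that, and SAP 7.10 places deviations in mITT. This subject appears to stay. The gap is therefore limited to subjects refused at confirmation.

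**Possible size (illustration).** The documents do not give the number of such subjects, k; I assume k = 0 to 5. The starting counts are also assumed: 43/50 to match the planned 86%, and 3/50 for a safety event. Intervals are exact, two-sided 95%.

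Primary rate after adding back k subjects: 43/(50 + k) if all are failures, (43 + k)/(50 + k) if all are successes.

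| k | All failures | All successes |
|---|---|---|
| 0 | 86.0% (73.3 to 94.2) | 86.0% |
| 1 | 84.3% (71.4 to 93.0) | 86.3% |
| 3 | 81.1% (68.0 to 90.6) | 86.8% |
| 5 | 78.2% (65.0 to 88.2) | 87.3% |

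Safety rate: (3 + k)/(50 + k) if each had the event, 3/(50 + k) if none did.

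| k | All had the event | None had the event |
|---|---|---|
| 0 | 6.0% (1.3 to 16.5) | 6.0% |
| 1 | 7.8% (2.2 to 18.9) | 5.9% |
| 3 | 11.3% (4.3 to 23.0) | 5.7% |
| 5 | 14.5% (6.5 to 26.7) | 5.5% |

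The extreme primary case, five failures, moves the rate by 86.0 − 78.2 = 7.8 points, against the plan's margin of 10.1. One excluded failure moves it by 86.0 − 84.3 = 1.7 points.

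**The case against.** The case on the other side is substantial, and it rules out several stronger readings.

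- *The same subject can be dropped or kept at will.* A reader might infer this from Protocol 9.7.2 and Protocol 13 together. The two can be read as covering different groups: consented but never confirmed, and confirmed but later found in breach. On that reading they do not conflict.
- *The person deciding has seen the outcome.* The documents do not show this. The primary endpoint and ENT are core-lab assessments, and nothing suggests that these reads are available at confirmation. Mortality and mRS are 90-day outcomes. At most the site has its own mTICI reading and early clinical course. Protocol 6.1 says only that a physician confirms, not that it is the operator.
- *A harmed subject can vanish from every table.* This goes too far. Protocol 7.1 and Table 7 state AE recording and reporting rules with no eligibility limit, so some of these AEs may still reach the sponsor, and SAP 7.6 does not confine its tables to mITT. SAP 7.2 makes the count derivable. Silence in SAP 7.2 does not formally cancel the summary in Protocol 9.7.2, and SAP 7.11 does not list it as a change.
- *The bias flatters the device.* Unproven: the tables above run both ways.

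The group may also be small. Criteria are checked at baseline (Protocol 6.2) and candidacy again at the pre-procedure angiogram (6.3). Most criteria are facts fixed before NIMBUS is used, and the Steering Committee can be consulted on eligibility (14.2).

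What remains is that exposed, consented subjects refused at confirmation have no place in any planned endpoint analysis, and that their AEs are not assured.

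**Conclusion.** The point holds in a limited form. Confirmation of eligibility can only be completed after NIMBUS exposure and has no deadline. Consented, exposed subjects who are refused at that step are outside mITT and outside the AE population of Protocol 7.3, and no endpoint analysis covers them. The documents permit selection after the site's own angiographic reading; they do not show that it happens.

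The size is unknown and is zero if there are no such subjects. Under the assumed counts, one to five of them would move an 86.0% primary rate to between 78.2% and 87.3%, and a 6.0% safety rate to between 5.5% and 14.5%. The gap matters more for the safety rates, where the exposed population is the natural denominator. It is worth correcting because the correction is cheap.

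**What to change.** 1. In Protocol 9.5 and SAP 5, add a Safety Analysis Set: all consented subjects in whom NIMBUS was introduced, regardless of eligibility. Use it for AEs (naming it in SAP 7.6), device deficiencies, ENT, sICH and mortality, alongside the mITT results.
2. In Protocol 7.3, replace the enrolled-and-eligible wording with that set.
3. Keep mITT as the primary set, and repeat the primary rate in all consented, NIMBUS-exposed subjects as a sensitivity analysis. Moving every late-found ineligible subject into mITT is not advised. It would change the primary population, for example by admitting first NIMBUS use after the third pass, which Protocol 4.1 and 6.3 make ineligible.
4. Carry the Protocol 9.7.2 summary of ineligible consented subjects into SAP 7.2 as a listing with the unmet criterion, the date of the eligibility decision and the core-lab mTICI.

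The cost is wording in both documents and one extra set of tables, with a safety set that includes a few subjects outside the target population. Every consented subject is already entered in the eCRF. SAP version 1 is dated January 2022 and the synopsis gives a study end of Q2 2021. If follow-up was already complete, item 2 cannot recover AEs that were not collected, but the SAP items remain useful.

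None of this addresses selection through who is approached for consent up to day 7.
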